# **8.5.3** Safety Population

The Safety Population will consist of all dispensed subjects and, for eye level summaries, both of their eyes. Subjects will be included in Safety summaries according to the treatment that they received. If a subject receives more than one treatment and one of those treatments is the Test solution, then the subject will be included in Safety Population summaries under the Test treatment group.

#### 8.6 Statistical Analysis

# **8.6.1** Methods of Analysis

#### 8.6.1.1 General Methods

Continuous data will be summarized using descriptive statistics: sample size, mean, standard deviation, median, minimum and maximum. Categorical data will be presented using the total counts for each category and corresponding percentages. The denominator for each percentage will be the number of subjects or eyes with non-missing data at the given visit for each respective study treatment, unless otherwise indicated.

As is customary for contact lens care product trials, eyes will be treated as independent sampling units in eye level analyses unless otherwise noted.

Further details will be provided in a separate statistical analysis plan which will be completed and approved prior to unmasking of the treatment assignments.

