#### Sample size calculations:

In a previous study (Bausch + Lomb study 872), the following outcomes were observed. These outcomes

serve as expected results for the current study.

- 1. Overall comfort averaged over all follow-up visits: standard deviation = 13.9 points
- 2. Dryness averaged over all follow-up visits: standard deviation = 13.9 points
- 3. Slit lamp findings greater than grade 2 at any follow-up visit were observed in 0.5% of eyes

When the sample size is 160 subjects per treatment group, the overall power of the trial will be 97%. To allow for losses of up to 13%, approximately 184 subjects will be enrolled per treatment group for a total of 368 subjects.

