### 3.1 Description of Study Design

Approximately 368 subjects (736 eyes) will be enrolled in this multicenter, randomized, masked, parallel, bilateral study at approximately 12-16 investigative sites in the United States (US). Approximately one-half of the eligible subjects will be randomized to receive Bausch + Lomb investigational BL-300-PFM04 Preservative Free Lubricating and Rewetting Drops, and approximately one-half of the subjects will be randomized to receive OPTI-FREE Replenish Rewetting Drops. In addition, all subjects will be dispensed two new pairs (1 to wear, 1 back-up) of their habitual lenses at the beginning of the study for daily wear. A third pair will be kept at the site for each subject.

All subjects will be seen for a Screening/Dispensing Visit, at which informed consent will be obtained and eligibility will be assessed. If eligible, subjects will be dispensed two new pairs of their habitual contact lenses and a Study Kit containing a supply of either the test or control rewetting drops, according to the subject's randomly assigned treatment. The subject will also be dispensed lens care products (Biotrue multi-purpose solution or Boston SIMPLUS® Multi-Action Solution and lens cases) sufficient for the entire study. Subjects must NOT use ANY other cleaning and disinfecting solution or rewetting drops during the study.

Subjects will be required to wear their study lenses for a minimum of 8 hours on a daily wear basis for 1 month and during wear, place 1-2 study rewetting drops in each eye at least 4 times per day. Subjects are to use the specified lens care products after removing the lenses each day. Subjects will return their full, partially full and empty rewetting drop bottles/single-use dispensers and worn and unworn lenses to the unmasked designee at the 1-month follow up/exit visit (or early discontinuation visit) for return to the Sponsor. It is not necessary to return any bottles of Biotrue multi-purpose solution or Boston SIMPLUS Multi-Action Solution or unused lens cases.

Eligible subjects will be enrolled into one of eight lens groups based on their habitual contact lenses. Subjects will be randomized on a 1:1 basis within each lens group per site to receive either the Test or Control rewetting drops. The eight lens groups will be comprised of habitual wearers of soft contact lenses or gas permeable contact lenses based on lens material as indicated in table below.

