# 8.3 Sample Size

Estimates of standard deviations and proportions were obtained from Bausch + Lomb Study #872.

The sample size calculations assume that the level of analysis will be the eye and that the outcomes from each subject's eyes will be independent. This is a standard assumption for contact lens care product trials.

The recommended minimum sample size is 20 Test group subjects per lens stratum. Therefore, with eight strata the targeted completed sample size will be (20 Test subjects/stratum + 20 Control subjects/stratum) x 8 strata = 320 subjects (assuming sufficient statistical power is provided by this sample size).

Sample size calculations were completed using nQuery Advisor® 7.0 software.

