#### **8.3.2** Overall Comfort

In Study 872, the standard deviation of overall comfort ratings averaged over all visits was 13.9 units. When the sample size in each group is 320 eyes (160 subjects), a two group 0.05 one-sided t-test will have 99% power to reject the null hypothesis that the test

is not non-inferior to the control (the difference in means,  $\mu_T$  -  $\mu_S$ , is -5 or farther from zero in the same direction) in favor of the alternative hypothesis that the test is non-inferior, assuming that the expected difference in means is 0 and the common standard deviation is 13.9.

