#### **8.3.4** Overall Power

If the primary endpoints are independent, the overall power of the study is  $99\% \times 99\% \times 99\% = 97\%$ .

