#### 8.4 Randomization

Subjects will be randomized to one of two treatment arms in a 1:1 ratio, using Test drops or Control drops for the duration of the study. Randomization will be managed using ORS. The randomization will be stratified by lens group within investigational site. The lens group will be determined by the subjects' habitual lens material at Screening/Dispensing and will be one of the groups shown in Table 1: Lens Groups (page 13).

Efforts will be made to enroll subjects in at least four of the lens strata within each site to minimize confounding between site and lens strata. It should be noted that while the target enrollment for each lens strata is approximately 40 subjects (approximately 20 per treatment arm), some lens strata may be difficult to enroll.

An unmasked statistician who is not otherwise involved in the trial will create the randomization schedule.

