#### 8.6.1.2 Graded Slit Lamp Findings

At each follow-up visit, graded slit lamp findings will be assessed for each eye using Grades 0 through 4. Using only the non-missing observations from all visits without imputation, each eye will be classified with respect to findings greater than grade 2 at any visit (Absent, Present). Missing data will not be imputed. Greater than grade 2 findings (Absent, Present) will be summarized at the eye level by treatment using categorical summary statistics for the Safety Set in a table. A one-sided upper 95% confidence limit around the difference in "Present" proportions between the test and control treatment groups will be constructed using the Newcombe-Wilson score method. If the upper confidence limit is less than 5.0%, then the null hypothesis that the test solution is not non-inferior will be rejected, and the test solution will be statistically successful in this outcome.

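### The primary limits treat a subject's two eyes as independent although subjects are randomised; if the eyes are positively correlated the limits are too narrow, and the stated power holds only at low correlation.

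*Combined protocol and SAP*

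**What the plan says.** The subject is the unit of randomisation. Section 3.1 states: "Subjects will be randomized on a 1:1 basis within each lens group per site to receive either the Test or Control rewetting drops". Section 8.4 adds: "The randomization will be stratified by lens group within investigational site". Section 3.1 also has each subject put the assigned drop in each eye, and inclusion criterion 7 requires the same brand of lens in both eyes.

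The unit of analysis is the eye. Section 8.6.1.1: "eyes will be treated as independent sampling units in eye level analyses unless otherwise noted". Nothing in 8.6.1.2 to 8.6.1.4 notes otherwise:

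- Slit lamp (8.6.1.2): "Greater than grade 2 findings (Absent, Present) will be summarized at the eye level by treatment", with a Newcombe-Wilson upper limit on the difference in those proportions.
- Comfort (8.6.1.3) and dryness (8.6.1.4): an eye-level analysis of variance with treatment and site as its only factors.

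No subject term, cluster variance or subject-level sensitivity analysis appears. The ITT sensitivity analysis changes the population and the handling of missing data, not the unit.

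The sample size follows the same rule. Section 8.3: "The sample size calculations assume that the level of analysis will be the eye", with the two eyes taken as independent. Section 8.3.2: "When the sample size in each group is 320 eyes (160 subjects), a two group 0.05 one-sided t-test will have 99% power"; section 8.3.3 repeats this for dryness. Section 8.3.4: "If the primary endpoints are independent, the overall power of the study is" 0.99 cubed, or 97%. The synopsis drops the condition: "When the sample size is 160 subjects per treatment group, the overall power of the trial will be 97" per cent. The only reason given for independence is that it is standard or customary in contact lens care trials.

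**The concern.** Both eyes of a subject receive the same drop, so between-subject variation does not cancel from the treatment comparison. Comfort and dryness are one person's ratings of two eyes under the same drop, lens brand, wear schedule and visit, so independence needs support, and none is offered beyond custom. With positive correlation the eye-level standard error is too small. Each primary decision rests on whether a one-sided 95% limit clears a margin, so a limit that is too narrow makes it easier to declare an inferior drop non-inferior. The stated power is also affected, because it counts 320 independent observations per arm.

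**Working it through.** **Inputs.** One-sided alpha 0.05 (synopsis); margin 5 points and expected difference 0 (8.2.2, 8.2.3, 8.3.2, 8.3.3); SD 13.9 (8.3.2, 8.3.3); 320 eyes = 160 subjects per arm (8.3.2); slit lamp rate 0.005 in both arms and margin 0.05 (8.2.1, 8.3.1). Rho is not given and is varied from 0 to 1. SD 13.9 is read as an eye-level SD, because 8.3.2 applies it to 320 eyes.

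**Reproducing the plan.** SE = 13.9 × √(2/320) = 1.10. The noncentral t with 320 per arm gives 99.8% power (stated 99%). Exact enumeration for slit lamp gives over 99.9% (stated 99%). 0.99³ = 97.0%. The plan's figures follow from its own assumptions.

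**Comfort and dryness with correlated eyes.** The mean of two eyes has variance 13.9² × (1+rho)/2, so with 160 subjects per arm the true SE is 1.10 × √(1+rho).

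- Actual error of the planned limit = 1 − Φ(1.645/√(1+rho)).
- Power of a test that truly holds 5%: noncentral t, 160 per arm, SD 13.9 × √((1+rho)/2).

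**Slit lamp.** The number of affected eyes among 160 pairs per arm was enumerated exactly, with the probability that both eyes are affected equal to p² + rho × p(1−p). Error is taken at 5.5% v 0.5%. The planned limit uses n = 320; the adjusted limit uses n = 320/(1+rho).

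**Overall power** is the plan's own product: (comfort or dryness power)² × adjusted slit lamp power. At rho 0.5: 0.9804² × 0.9995 = 0.961. At 0.8: 0.9590² × 0.9974 = 0.917. At 1.0: 0.9413² × 0.9953 = 0.882.

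| rho | True SE | Error, comfort or dryness | Error, slit lamp | Valid power, comfort or dryness | Overall power |
|---|---|---|---|---|---|
| 0 | 1.10 | 5.0% | 4.8% | 99.8% | 99.6% |
| 0.3 | 1.25 | 7.5% | 7.2% | 99.0% | 98.1% |
| 0.5 | 1.35 | 9.0% | 8.8% | 98.0% | 96.1% |
| 0.8 | 1.47 | 11.0% | 11.1% | 95.9% | 91.7% |
| 1.0 | 1.55 | 12.2% | 11.7% | 94.1% | 88.2% |

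At rho 0.1 and 0.2 the comfort or dryness error is 5.8% and 6.7%. It passes 10% only above rho of about 0.65. Valid power drops below 99% above about 0.31, and overall power below 97% above about 0.42. Slit lamp power is not a problem: it is at least 99.5% with the adjusted limit at every rho.

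**Partial offset from lens group.** Randomisation is stratified by lens group but the model omits it, which makes the planned standard error somewhat too large. This was simulated with 20,000 runs per setting, true difference −5 and 320 subjects. The 14 sites, four lens groups per site, blocks of two and the share of variance due to lens group are assumptions. Error of the planned analysis:

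| rho | No lens-group effect | 10% of variance | 20% of variance |
|---|---|---|---|
| 0.3 | 7.5% | 6.2% | 4.5% |
| 0.5 | 9.1% | 7.9% | 6.3% |
| 0.8 | 11.3% | 10.2% | 9.1% |
| 1.0 | 12.4% | 11.7% | 10.4% |

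The same model run on subject means rejected 4.8–5.3% with no lens-group effect, and 3.0–4.3% with a 10–20% effect.

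**The case against.** **The assumption is openly declared and customary, and a separate SAP is still to come.** This is a stated choice and not a contradiction or an arithmetic slip. But declaring it does not make a nominal 95% limit cover 95%, and nothing says that the SAP will change the unit.

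**The planned test itself keeps its power.** This is true in a narrow sense. At zero difference the uncorrected limit succeeds 99.5%, 99.1%, 98.5% and 98.0% of the time at rho 0.3, 0.5, 0.8 and 1.0, and stays at or above 99% up to about 0.56. It does so only because its error exceeds 5%. Sections 8.3.2 and 8.3.3 claim 99% for a 0.05-level test, and that claim fails above about 0.31.

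**The harm depends on an unknown rho, and lens group offsets part of it.** This stands as a limit on the size. At rho 0.3 with a 20% lens-group effect the error is below nominal. At higher rho the offset is incomplete.

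**All three endpoints must succeed (8.6.8).** This also stands. The per-endpoint errors become trial-level errors only for a drop at the margin on one endpoint that clearly passes the others. For a drop at −5 on both comfort and dryness with rho 0.8, both pass 1.2% of the time if the endpoints are independent, and 6.3% at an assumed endpoint correlation of 0.8.

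**Conclusion.** The concern holds and should be corrected before unmasking. As written, all three primary limits are anti-conservative whenever the two eyes are positively correlated, apart from the lens-group offset for comfort and dryness. Without that offset, per-endpoint error is about 7% to 12% for rho from 0.3 to 1.0. The stated 99% for comfort and dryness, and 97% overall, are attained by a valid test only up to rho of about 0.31 and 0.42. The overall figures use the plan's multiplication, which assumes independent endpoints; positive correlation between endpoints would raise them. The trial remains well powered, so the defect is in the stated error level and the stated power, not in the number of subjects. The conclusion rests on 13.9 being an eye-level SD and on an assumed range for rho.

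**What to change.** In 8.6.1.1 to 8.6.1.4:

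1. **Comfort and dryness:** run the analysis of variance on the mean of each subject's two eyes, or keep eye-level data with a subject random effect or cluster-robust standard errors. Use the same unit in the ITT multiple-imputation analysis.
2. **Slit lamp:** use a cluster-adjusted Newcombe-Wilson limit with effective n = eyes/(1 + estimated rho), which keeps the proportion-of-eyes hypothesis in 8.2.1. Only 320 × 0.005 = 1.6 affected eyes per arm are expected, so rho may not be estimable. Pre-specify a fallback of rho = 1 (effective n 160 per arm), which gives error of 0.6–4.5% and power of about 99.5% or more.
3. **Either-eye slit lamp analysis by subject:** supportive only, because it changes the estimand and the basis of the 5% margin and the 0.5% rate.
4. **Section 8.3 and the synopsis:** restate comfort, dryness and overall power for 160 subjects per arm over a stated range of rho.

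Eye-level tables can stay as descriptive summaries. The cost is protocol and SAP wording and a somewhat lower stated power. The slit lamp fallback is conservative when eyes are not fully concordant, and the subject-mean analysis is mildly conservative if lens group matters and stays out of the model. No extra subjects, visits or data are needed.

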#### 8.6.1.2 Graded Slit Lamp Findings

At each follow-up visit, graded slit lamp findings will be assessed for each eye using Grades 0 through 4. Using only the non-missing observations from all visits without imputation, each eye will be classified with respect to findings greater than grade 2 at any visit (Absent, Present). Missing data will not be imputed. Greater than grade 2 findings (Absent, Present) will be summarized at the eye level by treatment using categorical summary statistics for the Safety Set in a table. A one-sided upper 95% confidence limit around the difference in "Present" proportions between the test and control treatment groups will be constructed using the Newcombe-Wilson score method. If the upper confidence limit is less than 5.0%, then the null hypothesis that the test solution is not non-inferior will be rejected, and the test solution will be statistically successful in this outcome.

#### 8.6.1.3 Overall Comfort

At each follow-up visit, overall comfort will be assessed for each eye on a scale from 0 to 100, with 100 denoting the most favorable response. For each eye, mean overall comfort

over all follow-up visits will be computed as the average of the non-missing values over all scheduled follow-up visits. Missing data will not be imputed for the primary analysis. Mean overall comfort over all follow-up visits will be summarized at the eye level by treatment using continuous summary statistics for the Per Protocol Set in a table. A one-sided lower 95% confidence limit around the difference in means between the test and control treatment groups, computed using an analysis of variance model including the fixed factor of treatment and the fixed blocking factor of site, will be displayed. If the lower confidence limit is greater than -5, then the null hypothesis that the test solution is not non- inferior will be rejected, and the test solution will be statistically successful in this outcome.

As a sensitivity analysis, the ITT Population will be analyzed for this endpoint. Summaries by treatment and a confidence interval around the difference in means will be provided as described above using the available data. Twenty imputations of missing overall comfort data will be produced by treatment group using the Markov chain Monte Carlo (MCMC) method. The variables used to create the imputed datasets will be the overall comfort scores observed at each scheduled visit. The differences and standard errors estimated by imputation will be combined to create an estimated difference and confidence limit.

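### The comfort and dryness analyses treat a subject's two eyes as independent although drops are randomised by subject; lens group, a randomisation stratum left out of the model, should be added only when that is corrected

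*Combined protocol and SAP*

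**What the plan says.** Randomisation is by subject and stratified. Section 3.1 states "Subjects will be randomized on a 1:1 basis within each lens group per site", and section 8.4 states "The randomization will be stratified by lens group within investigational site". There are eight lens groups and about 12 to 16 sites. Section 8.4 also warns that "some lens strata may be difficult to enroll".

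The effectiveness model in section 8.6.1.3 is applied to each eye's mean score over follow-up visits, with the difference and its limit "computed using an analysis of variance model including the fixed factor of treatment and the fixed blocking factor of site". The synopsis gives the same model, and section 8.6.1.4 applies the same methods to dryness. Neither a lens group term nor a subject term appears.

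On the unit of analysis, section 8.6.1.1 says "eyes will be treated as independent sampling units in eye level analyses unless otherwise noted", and sections 8.6.1.3 and 8.6.1.4 note no exception. Section 8.3 bases the sample size on the premise that "the level of analysis will be the eye" and that a subject's eyes are independent. Both sections describe this as usual for contact lens care product trials. Section 8.3.4 then multiplies three powers: "If the primary endpoints are independent, the overall power of the study is" 97%.

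**The concern.** The planned SE matches neither the unit that was randomised (the subject) nor the strata within which randomisation took place.

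- **Eye pairing.** Both eyes of a subject receive the same drops and are rated by the same person. If their scores are positively correlated, 320 eyes carry less information than 320 independent observations. The SE is then too small. In a non-inferiority test that lets an inferior product pass more often than the nominal 5%.
- **Lens group.** Stratification takes lens-group variance out of the treatment difference, at least in part, but a site-only model leaves it in the residual. That makes the SE too large, which is conservative.

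The two errors pull in opposite directions, so correcting lens group alone would make matters worse. The intent-to-treat (ITT) sensitivity analysis uses the same model and would not reveal the problem.

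**Working it through.** **Inputs from the documents.** Standard deviation (SD) 13.9 for both endpoints, and 320 eyes (160 subjects) per group (8.3.2, 8.3.3). Margin 5 and one-sided alpha 0.05 (synopsis). True difference 0 for power. Slit lamp power 99% (8.3.1).

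**Assumed, because the documents do not give them.** Between-eye correlation rho 0.5 to 0.9 (total, including the lens-group part). Lens-group share of variance s 0 to 20%. The SD of 13.9 is read as the within-site SD per eye.

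**1. The plan's own figure.** With independent eyes, SE = 13.9 × √(2/320) = 1.099. Power = Φ(5/1.099 − 1.645) = 99.8%, which the plan states as 99%. The product 0.99³ = 0.970 matches the stated 97%. The calculation reproduces, but only with independent eyes.

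**2. Large-sample variances.** Let V = 13.9² × 2/160 = 2.415. With lens group fully balanced:

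- true variance of the difference: V[(1 + rho)/2 − s]
- reported, as planned: V/2
- reported, eyes independent plus lens group: V(1 − s)/2
- reported, subject means with site only: V(1 + rho)/2
- reported, subject means with site and lens group: V[(1 + rho)/2 − s], equal to the true variance

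One-sided error at a true difference of −5 is Φ(−1.645 × reported SE/true SE).

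- rho 0.9, s 0: true SE = √(2.415 × 0.95) = 1.515; 1.645 × 1.099/1.515 = 1.193; error 11.6%.
- rho 0.5, s 20%: true SE = √(2.415 × 0.55) = 1.153; 1.645 × 1.099/1.153 = 1.568; error 5.8%.

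| s | rho | As planned | Eyes independent + lens group | Subject means, site only | Subject means, site + lens group |
|---|---|---|---|---|---|
| 0 | 0.5 | 9.0% | 9.0% | 5.0% | 5.0% |
| 0 | 0.9 | 11.6% | 11.6% | 5.0% | 5.0% |
| 5% | 0.5 | 8.2% | 8.8% | 4.4% | 5.0% |
| 5% | 0.9 | 11.0% | 11.6% | 4.6% | 5.0% |
| 10% | 0.5 | 7.5% | 8.6% | 3.9% | 5.0% |
| 10% | 0.9 | 10.4% | 11.6% | 4.1% | 5.0% |
| 20% | 0.5 | 5.8% | 8.0% | 2.7% | 5.0% |
| 20% | 0.9 | 9.0% | 11.5% | 3.2% | 5.0% |

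The planned error is never above that of the eye-level model with lens group added. So all of the inflation comes from pairing, and leaving out lens group reduces it.

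**3. Where the plan would be conservative.** The ratio of reported to true variance under the plan is 1/(1 + rho − 2s), which equals 1 at rho = 2s. At s 20% the large-sample error is 5.0% at rho 0.4 and 4.15% at rho 0.3. At trial size, small strata balance lens group only partly, so the offset is weaker. Two simulation checks at s 20%, rho 0.4 gave about 5.6% and 6.0%. The break-even correlation therefore lies below 2s in this trial.

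**4. Simulation at trial size.** 368 enrolled, 13% lost at random, 12 or 16 sites, four or eight lens groups open per site, blocks of 2 or 4, equal or uneven lens groups, s 5 to 20%, rho 0.5 to 0.9. The planned test gave 6.4% to 12.0%. Eyes independent plus lens group gave 7.8% to 12.4%. Subject means with site only gave 3.2% to 4.8%. Subject means with site and lens group gave 4.7% to 5.3%, or 4.5% to 5.3% with the two smallest groups pooled.

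**5. Power after correction.** Power = Φ(5/SE − 1.645). SE 1.515 gives 95.1%, and SE 1.153 gives 99.6%. By the plan's product rule with slit lamp kept at 99%: 0.951² × 0.99 = 0.895 and 0.996² × 0.99 = 0.982, so about 90% to 98% overall.

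**6. Size on the score scale.** Non-inferiority is met when the observed difference exceeds −5 + 1.645 × SE. As planned that is −5 + 1.645 × 1.099 = −3.19. Corrected, it lies between −3.10 (SE 1.153) and −2.51 (SE 1.515).

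**The case against.** **Independent eyes are a declared convention.** True: sections 8.3 and 8.6.1.1 say so openly. Custom does not set the correlation to zero, however, and the plan offers neither an estimate of it nor an analysis that allows for it.

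**A separate statistical analysis plan is promised before unmasking.** It could contain a clustered analysis, and that cannot be excluded. But section 8.6.1.3 already fixes the model, the eye-level summary and the decision rule, so a plan written to this text would inherit them.

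**The size rests on assumed inputs.** This stands. With rho at least 0.5 and s at most 20%, every large-sample cell lies above the break-even, so an error above 5% follows from the chosen range. The documents cannot confirm the range.

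**Lens group is a minor matter.** This also stands. A reader might infer that omitting a stratification factor itself raises the false non-inferiority rate, or causes part of the inflation. The algebra shows the opposite: taken alone, the omission is conservative. In simulation, adding lens group at subject level gained only 0.1 to 2.1 power points for s 5 to 20%, and at s 0 it cost up to 0.2.

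**Few results would change verdict.** Only observed differences between about −3.2 and −2.5 are affected at most. The error rates are per endpoint at a true difference of exactly −5, whereas success requires all three primary endpoints (8.6.8). This limits the practical size but does not make the planned SE valid.

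**Conclusion.** The point holds for eye pairing. With positive between-eye correlation, the comfort and dryness tests use an SE that is too small for the randomised unit. For rho 0.5 to 0.9 and s 0 to 20%, the planned large-sample one-sided error is about 5.8% to 11.6% per endpoint. Omission of lens group partly offsets this. The plan could be conservative overall only if rho is below about 2s in large samples, and lower still at trial size.

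Two stronger readings are not supported. A reader might infer that the plan is certainly anti-conservative, but the documents give neither rho nor s. A reader might also infer that the trial is underpowered, but large-sample power per effectiveness endpoint stays at about 95% or more over the assumed range. The main consequence is for the error rate of the non-inferiority claim, with a restated power as a by-product.

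The change is worth making as a joint correction. Confidence is medium because both key quantities are assumed.

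**What to change.** - **Model.** In section 8.6.1.3 (which 8.6.1.4 follows) and the synopsis, analyse the subject mean of the two eyes, or keep eyes and add a random subject effect. Use fixed treatment, site and lens group, with lens group as a main effect. Do not add lens group while eyes are still treated as independent. If lens group is left out on purpose, say why.
- **Sparse groups.** Set a pooling rule before unmasking, for example that any lens group below a stated count joins the closest material class.
- **ITT sensitivity analysis.** Use the same model. The current imputation rule is "The variables used to create the imputed datasets will be the overall comfort scores observed at each scheduled visit", run by treatment group. Keep a subject's two eyes together in it. Adding site and lens group to the imputation is optional: with 12 to 16 sites and eight lens groups imputed by arm, sparse cells are a real risk.
- **Power.** Restate 8.3.2 to 8.3.4 and the synopsis without independent eyes.

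**Cost.** No new data. Lens group uses about 7 of roughly 303 to 307 subject-level residual degrees of freedom. The reported SE rises from about 1.10 to between 1.15 and 1.52, and the stated power will usually be lower. Overall power exceeds 97% only at the favourable end of the range, because the plan rounds 99.8% down to 99%.
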